Hepatobiliary tumors globally are the fifth-most common cause of cancer and the second leading cause of cancer death.[1] In the United States in 2015, there are expected to be 46,570 hepatobiliary malignancies with 28,250 deaths. Hepatocellular carcinoma (HCC) is the most common type of hepatobiliary tumor. The primary risk factors for HCC are chronic hepatitis B and C infections, although cirrhosis of any cause increases the risk. The rising incidence of hepatitis C has caused HCC to become one of the fastest-growing cancers in terms of incidence and death in North America.[1] Surgical resection and liver transplantation offer the best outcomes, with 5-year overall survival (OS) rates of 50-85%.[2-5] Unfortunately, many HCC patients are not candidates for surgical resection due to the presence of locally advanced disease or medical comorbidities. In addition, only select patients with early stage HCC (tumors <5 cm) are candidates for liver transplantation.[6] For patients who are not surgical candidates or who refuse surgery, a variety of nonsurgical treatment modalities are available, including radiofrequency ablation (RFA), transarterial chemoembolization (TACE), radioembolization (Y-90), chemotherapy (primarily sorafenib-based), and radiation therapy (RT). TACE, RFA, and RT can be used as “bridging” therapies to prevent disease progression in patients awaiting transplantation. However, to date, there have been no randomized trials comparing these modalities. A discussion at a multidisciplinary tumor board where physicians from each respective specialty of surgery, interventional radiology, radiation oncology, hepatology, and radiology often determines which modality is pursued. Similarly, the other hepatobiliary tumors, namely cholangiocarcinoma and gallbladder cancer, are primarily treated with surgery if possible. An additional indication for focal liver radiation therapy exists in patients with oligometastases from certain primary malignancies, such as colon, lung, or breast cancer.

Historically, the use of radiation in cancers of the liver was limited due to the risk of radiation-induced liver disease (RILD), which is characterized by anicteric ascites and elevated transaminase levels. No standard method of reversing RILD is known, and it can lead to fatal liver failure. The risk

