Significant variability in liver function is present in the population of patients with liver tumors and cirrhosis. Different models for grading the severity of cirrhosis are available, including the Child-Turcotte-Pugh (CTP) and Model for End-Stage Liver Disease (MELD) score. To date, CTP score has been the preferred scoring system in evaluating patients for consideration of SBRT. There are other staging and prognostic scores for patients with HCC including the AJCC stage, BCLC stage, CLIP score, and ALIBI score. The CTP score is based on the levels of bilirubin, albumin, and PT/INR; it also incorporates a subjective grading system for ascites and encephalopathy. The range of scores is 5 to 15, with scores 5-6 classified as CTP A, 7-9 CTP B, and 10-15 CTP C.[13] The risk of side effects has been suggested to increase with higher CTP scores. In the study by Choi et al, 75% of their patients had CTP A disease, and there were no grade 3 toxicities reported in their trial. [11] One-third of patients in the phase I/II trial at Indiana University experienced grade 3 hematologic or hepatic toxicity, although 17 out of 21 of those patients had pre-treatment grade 2 dysfunction in that category. In addition, there were 4 patients who had progressive liver dysfunction, 2 of whom went on to liver transplantation and the other 2 who died as a result of liver failure. All 4 of these patients had CTP \geq B8, and 2 of those patients were treated with 42 Gy in 3 fractions, which was concluded to be unsafe in CTP B patients.[10]

In addition to baseline liver dysfunction, many of the patients who are referred for liver SBRT have had prior therapies such as surgical resection, chemotherapy, RFA, TACE, or conventional radiotherapy, which can adversely affect liver function. A recent retrospective study from Michigan comparing their institutional experience of SBRT with RFA found that patients who were treated with SBRT were more likely to have received prior liver-directed therapies with a median of 2 treatments in SBRT patients compared to 0 in RFA patients.[14]

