4.5 Secondary Endpoints

1. The rate at which the theragnostically planned radiation plan is chosen as the actual treatment plan rather than the conventionally planned radiation plan.

2. LC, PFS, OS, time to transplant, distant liver failure, and time until salvage treatment
3. Post treatment changes in liver function tests and CTP score. We plan to document the rate of decline of CTP class as well as the rate of any grade of hepatic toxicities.

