11.0 TOXICITIES TO BE MONITORED/DOSAGE MODIFICATIONS

All subjects will have laboratory evaluation prior to initiation of treatment. This includes CBC with differential, platelets, CMP, and INR.. Radiation treatment will be suspended in subjects who develop new ascites (as indicated by abdominal ultrasound, CT scan, or physical exam) or encephalopathy. If the patient's clinical status is borderline and the treating physician determines a treatment break is necessary, re-evaluation for further treatment can occur 1-2 days later.

	CTP-A	CTP-B7
Total Bilirubin	<3	<4
Albumin	>2.5	>2.5
INR	<1.5X upper normal	PT > 6 seconds above normal
ANC	>1000	>1000
Platelets	>50,000	>50,000
Hgb	>9	>9
Ascites	none	none
Encephalopathy	none	none

The subject will be seen at least once weekly during treatment for assessment of side effects. The most current version of Common Terminology Criteria for Adverse Events (CTCAE) will be used for grading toxicity.

For the purposes of this study, we will monitor the following:

- Labs: AST, ALT, Alkaline phosphatase, bilirubin, INR, platelets, albumin, lymphocytes, sodium
- Hepatobiliary disorders: hepatic failure, hepatic hemorrhage, hepatic necrosis, hepatic pain, perforation of bile duct, portal hypertension, portal vein thrombosis, bile duct stenosis, biliary fistula, cholecystitis, gallbladder fistula
- Gastrointestinal disorders: ascites, duodenal hemorrhage, duodenal obstruction, duodenal perforation, duodenal stenosis, duodenal ulcer, gastric necrosis, gastric perforation, gastric stenosis, gastric ulcer
- Nervous system disorders: encephalopathy
- Musculoskeletal and connective tissue disorders: chestwall pain
- Renal and urinary disorders: acute kidney injury

A copy of the most current CTCAE version is available at <http://ctep.cancer.gov/reporting/>

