13.0 STATISTICAL METHODS

13.1 General Considerations

Statistical analysis of this study will be the responsibility of the Department of Biostatistics at Indiana University School of Medicine. Parameter estimates and relevant summary statistics will be reported for both efficacy and safety outcomes. Continuous variables will be summarized by means, medians, minima, maxima and standard deviations. Categorical variables will be summarized by frequencies and percentages. Missing data will not be imputed. Additional exploratory analysis will be conducted when appropriate. Changes from the analysis plan will not require an amendment to the protocol unless it changes a significant feature in the protocol. The statistical analysis methods are outline below.

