13.7 Analysis of Secondary Objectives

The rate at which the plan that utilized the HIDA scan is chosen for the actual treatment will be summarized along with the corresponding exact 95% Binomial confidence interval.

For Local Control, PFS, OS, time to transplant, time to distant liver failure, and time to salvage treatment, the median and the corresponding two-sided 95% confidence intervals will be calculated using the Kaplan-Meier method. Estimates and 95% confidence intervals will also be provided for 6 and 12 months. Local control will be evaluated using RECIST 1.1 criteria.

Changes in liver function tests using HIDA scans, standard blood tests and CTP score will be calculated and summarized. Additionally, all safety data will be listed. For the treatment-emergent AEs, namely AEs started or worsened during the on-treatment period, the incidence will be summarized by system organ class and/or preferred term, severity based on CTCAE grades, type of adverse event and the relation to the study drug. Deaths reportable as SAEs and non-fatal serious adverse events will be listed by and tabulated by type of adverse event. This will be done with the safety set.

Changes in liver volume in the treated and untreated segments will be summarized by basic summary statistics.

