17.3 Adverse Event (AE) and Serious Adverse Event (SAE) Reporting

Adverse events (AEs) will be recorded from the time of first study intervention and throughout the follow up period. All AEs considered related to the study intervention will be followed until resolution, return to baseline, or deemed clinically insignificant, even if this occurs post-study. Any death occurring within 30 days after the last study intervention must be reported as an SAE regardless of attribution.

17.3.1 Reporting to the IRB:

1. Unanticipated problems involving risks to subjects or others will be reported promptly to the IRB if they:
 - Unexpected;
 - Related or possibly related to participation in the research; and
 - Suggests that the research places subjects or others at a greater risk of harm than was previously known or recognized.

If the serious adverse event does not meet all three (3) criteria listed above, the event does not have to be promptly reported to the Indiana University IRB. However, it should be reported at the time of continuing review

2. Prompt reporting of unanticipated problems to the IRB is defined as within 5 days from becoming aware of the event.

17.3.2 Reporting to the Data Safety Monitoring Committee (DSMC):

Regardless of study sponsorship, this study is subject to monitoring by the Indiana University Simon Cancer Center Data Safety Monitoring Committee (DSMC). The DSMC chair and/or coordinator will review all expedited SAE reports through OnCore®. Expedited reports are completed per IRB guidelines and may include the IRB prompt reporting form, non-compliance form, AdEERS reports, MedWatch, and additional SAE forms as required by the sponsor. Submission of this information to the DSMC is additional to any other protocol-specified regulatory bodies (e.g., FDA, pharmaceutical company) to be notified. When follow-up information is received, a follow-up report should also be created in OnCore®. The DSMC chair and/or coordinator will review expedited SAE reports monthly and report findings to the DSMC quarterly.

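### AE incidence is specified only for an undefined on-treatment period and no post-treatment CTP score is scheduled, although secondary endpoint 3 needs both

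*Combined protocol and SAP*

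**What the plan says.** - **Endpoint (4.5).** Secondary endpoint 3 is about change after treatment in liver tests and CTP score. It adds: "We plan to document the rate of decline of CTP class as well as the rate of any grade of hepatic toxicities".
- **Collection (17.3).** "Adverse events (AEs) will be recorded from the time of first study intervention and throughout the follow up period". Section 8.5 has toxicity assessed at the 3, 6 and 12-month visits.
- **AE analysis (13.7).** "For the treatment-emergent AEs, namely AEs started or worsened during the on-treatment period, the incidence will be summarized by system organ class" and/or preferred term, with CTCAE grade and relationship. The same section lists all safety data, tabulates serious events without an on-treatment limit, and summarizes changes in HIDA values, blood tests and CTP score.
- **General rule (13.1).** "Parameter estimates and relevant summary statistics will be reported for both efficacy and safety outcomes". It names no AE table and no window.
- **CTP schedule.** The calendar (section 10) marks the CTP/MELD/ALBI row at baseline and midway through RT only. Section 8.3 links the midway labs to those scores. Sections 8.4 and 8.5 list labs but name no score.

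**The concern.** Section 3.0 gives less hepatotoxicity after treatment as a reason for HIDA-guided planning, and endpoint 3 is where the trial reports it. Two parts of the plan do not reach the period that the endpoint concerns.

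First, the only AE incidence table that 13.7 specifies is limited to a period with no stated start or end. The usual meaning of on-treatment leaves out follow-up. Second, 13.7 promises a summary of CTP change, but no score is scheduled after mid-treatment, and 13.7 does not mention the class-decline rate at all.

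The two gaps meet at ascites and encephalopathy. Both are CTP items: the Background says of the score that "it also incorporates a subjective grading system for ascites and encephalopathy". Ascites is also part of the protocol's own description of "radiation-induced liver disease (RILD), which is characterized by anicteric ascites and elevated transaminase levels". A non-serious case first arising in follow-up would be outside the AE table on the usual reading, and no scheduled CTP score would pick it up.

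If the plan is left as it is, the window for the hepatic toxicity rate will be chosen after the data are seen.

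**Working it through.** The plan gives no figure on this point. Its one set of design figures, the 3-of-15 rule in 13.4, reproduces by the exact binomial tail (0.873 against the stated 0.87 at a true rate of 30%) and does not bear on this issue.

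**1. Length of the window, if it means first to last fraction (assumption).** Section 9.4 gives 3 or 5 fractions, at least 48 hours apart, extendable to weekly. Span in days = (fractions − 1) × gap + 1.

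| Fractions | Gap (days) | Span (days) |
|---|---|---|
| 3 | 2 | 2 × 2 + 1 = 5 |
| 5 | 2 | 4 × 2 + 1 = 9 |
| 3 | 7 | 2 × 7 + 1 = 15 |
| 5 | 7 | 4 × 7 + 1 = 29 |

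The range is 5 to 29 days.

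**2. Earliest scheduled toxicity assessment after RT.** The visit at about 30 days is laboratory only (8.4 and the calendar), so the first assessment is the 3-month visit. Take 3 months as 91 days and use the 30-day visit tolerance.

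- Calendar anchor (months after RT): 91 − 30 = 61 days after the last fraction.
- Section 8.5 anchor (months after the end-of-treatment visit, earliest day 30 − 7 = 23): 23 + 91 − 30 = 84 days.

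Both exceed 0, and both exceed 30. All 3 of 3 follow-up assessments therefore fall after the window, even if a 30-day tail is assumed. Inclusion depends on onset: an event that began inside the window and is reported at a later visit still counts.

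**3. Which events are left out.** Serious events are tabulated and laboratory changes summarized without the limit. What remains is late-onset non-serious AEs, mainly the terms in section 11 that are not laboratory values.

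- Hepatobiliary: the seven in "Hepatobiliary disorders: hepatic failure, hepatic hemorrhage, hepatic necrosis, hepatic pain, perforation of bile duct, portal hypertension, portal vein thrombosis", plus cholecystitis, stenosis of the bile duct, and fistulas of the biliary tract and of the gallbladder: 7 + 4 = 11.
- Ascites, filed under gastrointestinal disorders: 1.
- "Nervous system disorders: encephalopathy": 1.

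Total: 11 + 1 + 1 = 13 terms.

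**4. Effect on the tabulated rate.** The denominator is the safety set (13.3.2). If all 20 enrolled subjects are treated, each subject whose only hepatic AE falls in the gap lowers the rate by 1/20 = 5 percentage points. The documents give no onset times, so the number of such subjects cannot be estimated.

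**5. CTP after treatment.** There are four post-treatment visits (about 30 days; 3, 6 and 12 months). CTP is marked at 0 of 4. Its inputs are bilirubin, albumin, PT/INR, ascites and encephalopathy (Background). At 3, 6 and 12 months, section 8.5 collects CMP, INR, a physical exam and a toxicity assessment, and section 11 monitors both clinical items, so the score can largely be derived. At the 30-day visit only labs are named, which does not support a full score.

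**The case against.** The strongest reply is that the exclusion is conditional. The documents never say that the on-treatment period ends at the last fraction. Endpoint 3 is expressly post-treatment and 17.3 records AEs through follow-up, so 13.7 could be read to match. Nor does 13.7 say that its treatment-emergent table is the only AE incidence output, and 13.1 promises summaries of safety outcomes. This partly stands: what is certain is that the window is undefined, and the 5-to-29-day figure rests on the usual reading. But 13.7 is the specific rule, 13.1 sets no window, and no text extends on-treatment to follow-up. If that extension is intended, one sentence would settle it.

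Second, CTP is a derived score and its inputs are collected, so the blank cells may be a calendar omission. That largely stands for 3, 6 and 12 months and is why the fix is cheap. Yet section 8.3 shows that the protocol names the scores where it wants them, and 13.7 specifies no class-decline analysis. The silence of 8.4 is weak evidence, because its list ends in an empty item; the calendar makes the point without it.

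Third, this is a descriptive pilot of 20 subjects. With a complete listing, anyone can count a rate over any window, and several of the 13 terms may often meet the seriousness criteria and be tabulated anyway. Treating ascites and encephalopathy as hepatic is also a choice, since section 11 files them elsewhere. All of this lowers the importance. It does not supply a pre-specified analysis for a named secondary endpoint.

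**Conclusion.** The concern holds and should be fixed. Followed as written, section 13.7 and the calendar give endpoint 3 no specified any-grade hepatic rate that clearly covers the post-treatment period, and no scheduled post-treatment score from which to report CTP class decline.

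The AE gap is confined to non-serious events with onset after the window. It assumes that on-treatment means first to last fraction, though a 30-day tail would still reach none of the three follow-up assessments. The CTP gap needs no such assumption: it is read directly from the calendar.

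The defect lies in what is specified. The data are collected and listed, so a full-period rate can still be produced. The primary endpoint, the sample size and the 3-of-15 rule are unaffected.

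**What to change.** In 13.7:

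- Tabulate AE incidence by grade in the safety set for events that start or worsen from the first fraction through the last follow-up visit. Include an any-grade hepatic row.
- State which section 11 terms make up that row, including whether ascites and encephalopathy belong to it.
- If a separate on-treatment table is kept, define its start and end.
- Report change from baseline in CTP score, and the rate of CTP class decline, at 3, 6 and 12 months.

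In section 10:

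- Mark the CTP/MELD/ALBI row at 3, 6 and 12 months, derived from the labs, exam and toxicity assessment already listed in 8.5. Endpoint 3 needs only CTP; the other two scores share the row.
- As housekeeping, show the follow-up toxicity assessment in the calendar so that it agrees with 8.5.

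The cost is SAP wording and calendar marks. No visit or test is added.

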13.8 Analysis of Exploratory Objectives

To assess the correlation between the radiation dose and the risk of RILD, graphs and descriptive statistics will be used to see if any relationships may exist.

Spearman's correlations will be used to compare output from each of the HIDA and fMRI scans to see if any measures correlate to each other.

To assess significant change in HIDA and fMRI scans, the plan based off the HIDA scan done at mid-therapy would be re-optimized, retrospectively. The proportion of patients who have a change in the regional distribution of function after the initial radiation treatments will be determined. If this re-optimized plan reduces the functional liver exposed to <15 Gy by 5% or more, this would be considered significant and will provide a potential idea about the feasibility of potential adaptive radiotherapy.

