4.6 Exploratory Endpoints

1. Correlations between radiation dose to the normal liver and the risk of RILD.
2. Correlation between the quantitative data from fMRI and HIDA scan values. Also, a preliminary exploration of the doses at which changes in fMRI are seen.
3. The rate at which the HIDA changed enough such that the radiation plan could have been adapted to decrease the amount of functional liver receiving >15 Gy.

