8.3 Radiation Treatment Period

During radiation treatment, subjects will be seen at least once per week for clinical assessment that will include a limited physical exam and assessment of toxicity.

Midway through radiation treatment, subjects will have the following procedures:

1. Laboratory Assessments (CBC with differential, CMP, INR) for assessment of CTP, MELD, and ALBI scores.
2. HIDA scan

Subjects who have a total of 3 fractions will have Midway Assessments done after fraction 2. Subjects who have a total of 5 fractions will have Midway Assessments after fraction 3.

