9.4 Radiation Planning

Standard Target Contouring guidelines

1. GTV is contoured based on CT obtained during simulation and any previous CT, MRI, or PET scans.
2. The internal target volume (ITV) will account for tumor motion as seen on 4D-CT. Viewing the lesion on individual phases may be necessary in order to adequately delineate the lesion.
3. The planning target volume (PTV) will account for set-up error and will be created by expanding the ITV 1 cm cranio-caudally and 0.5 cm radially, unless less motion can be documented on simulation scans.

Contouring from the HIDA scan

1. Based on the HIDA scan data, contours of relative functional liver will be created based on the following thresholds of maximum intensity: 0-25% maximum, 25-100% maximum, 50-100% maximum, 75-100% maximum. These structures will serve as avoidance structures in the design of radiation fields for theragnostic SBRT planning.

Standard SBRT

The standard SBRT prescription, planning, constraints, and treatment parameters are as follows:

1. Prescription:
3- or 5-fraction SBRT will be utilized in this study depending on clinical scenario. It is recommended that subjects without cirrhosis or with CTP A disease are treated with 3 fractions and those with CTP B cirrhosis are treated with 5 fractions. The dose range typically will be from 4000-5400 cGy delivered over 3-5 fractions.
2. Planning:
SBRT; IMRT if constraints not met or for additional functional sparing.

3. SBRT Constraints:

Structure	Volume	Dose / Constraint
PTV	>95%	Rx
GTV	>98%	>110% Rx
Liver – GTV	700cc or V10 Gy	<1500cGy or <70%
	1/3 uninvolved	<1000cGy (CTP-A), <1800cGy (CTP-B7)
	500cc uninvolved	<700cGy (CTP-A), <1200cGy (CTP-B7)
Duodenum	0.5 cc	2400 cGy (3 fraction) 3000 cGy (5 fraction)
	<5 cc	1650 cGy (3 fraction) 1800 cGy (5 fraction)
	<10 cc	1140 cGy (3 fraction) 1250 cGy (5 fraction)
Stomach	0.5 cc	2250 cGy (3 fraction) 3000 cGy (5 fraction)
Esophagus	0.5 cc	32 Gy (5 fx)
Spinal Cord	100%	<600cGy/fraction
Chest Wall	.5 cc	<5000cGy (5 fraction)
	<5cc	4000cGy (3 fraction)
	<30cc	3000cGy
R Kidney	2/3	<2000cGy
L kidney	1/3	<1500cGy
Heart	0.5 cc	3000 cGy (3 fraction) 5250 cGy (5 fraction)

a. Variation acceptable constraints (per RTOG 1112)

Structure	Variation acceptable	Deviation unacceptable
Esophagus max (0.5 cc)	>32 but ≤34 Gy	>34 Gy
Stomach max (0.5 cc)	>30 but ≤32 Gy	>32 Gy
Duodenum max (0.5 cc)	>30 but ≤32 Gy	>32 Gy
Small bowel max (0.5 cc)	>30 but ≤32 Gy	>32 Gy
Large bowel max (0.5 cc)	>32 but ≤34 Gy	>34 Gy

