10.0 STUDY CALENDAR

	Baseline	Post-Consult	Mid way through RT	End of treatment visit	Follow up
	-4 weeks of Registration	After consult and prior to treatment	Fraction 2 or 3 ^A	30 ± 7 days post last treatment	3, 6, and 12-month post-RT
Informed Consent	X				
History	X				
Physical	X				X ^B
Vitals (ht, wt, bp)	X				X
Clinical Assessment			X ^C		
ECOG score	X				X
CBC w/ diff, platelets, CMP, INR	X		X ^D	X	X
AFP or CEA as indicated	X				X
Urine pregnancy test	X ^E				
CTP, MELD, and ALBI scores	X		X		
CT Simulation Scan		X			
MRI with Eovist of abdomen and/or Triple Phase ABD CTG		X ^F			X
HIDA scan		X ^F	X		X

^A Subjects who have a total of 3 fractions will have Midway Assessments done at fraction 2. Subjects who have a total of 5 fractions will have Midway Assessments at fraction 3.

^B Physical Exam required for Follow up visits. History not required.

^C Subjects will be seen at least once per week during their course of RT for clinical assessment. This will include a limited physical exam and toxicity assessment.

^D Labs may be monitored more frequently per the treating physician's discretion.

^E Only required in female subjects of child bearing potential

^F HIDA or Eovist MRIs obtained prior to consult can be used if performed within 8 weeks of simulation.

^G Imaging evaluation to be determined by treating MD depending on patient's clinical situation. For Ex: some patients may have a contraindication to a certain imaging modality (e.g. CT contract allergy). As long as the patient undergoes follow-up imaging, the use of CT vs. MRI for imaging follow up will not be considered a protocol deviation

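### The mid-treatment adaptation endpoint does not say how to treat dose already delivered or which plan is the comparator, so its rate may misstate how often adaptation was possible

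*Combined protocol and SAP*

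**What the plan says.** Section 4.6 sets the third exploratory endpoint as "The rate at which the HIDA changed enough such that the radiation plan could have been adapted to decrease the amount of functional liver receiving" more than 15 Gy.

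Section 13.8 gives the scoring method: "the plan based off the HIDA scan done at mid-therapy would be re-optimized, retrospectively". The criterion follows: "If this re-optimized plan reduces the functional liver exposed to <15 Gy by 5% or more, this would be considered significant". The result is offered as a tentative indication of whether adaptive radiotherapy is feasible.

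On timing, section 8.3 states: "Subjects who have a total of 3 fractions will have Midway Assessments done after fraction 2". For the longer course it states: "Subjects who have a total of 5 fractions will have Midway Assessments after fraction 3". Footnote A of the study calendar (section 10.0) words it differently: "Subjects who have a total of 3 fractions will have Midway Assessments done at fraction 2", and likewise for fraction 3 of 5.

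No section says whether the re-optimized plan covers the whole course or only the remaining fractions, whether delivered dose is added in, whether the 15 Gy line is cumulative, or which plan the 5% reduction is measured against.

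**The concern.** The endpoint is a counterfactual: at the time of the scan, could a change of plan still have kept functional liver below 15 Gy? By then most of the course has been given. The 15 Gy formula in section 4.4 is applied to complete plans, so an analyst could naturally carry that habit into 13.8 and compare one whole-course plan with another. That comparison describes a dose distribution in which the new plan had been used from the first fraction. A subject could be classed as adaptable, or as not adaptable, on a dose that could no longer be delivered.

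At stake is the interpretation of one exploratory rate that is meant to inform later work on adaptive planning. With the 15 evaluable subjects targeted in section 13.4, reclassifying one subject moves that rate by 1/15 = 6.7 percentage points.

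**Working it through.** **Inputs.** Fractions given at the scan: 2 of 3 or 3 of 5 (section 8.3). Threshold: 15 Gy (sections 4.6 and 13.8). Typical prescription: 40 to 54 Gy (section 9.4). Assumption: equal fractions, each with the same spatial distribution.

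**The plan's own figures.** None is stated for this endpoint. The only computed design figures are in the table in section 13.4 and concern the primary endpoint. They reproduce: the probability of at least 3 of 15 at a true rate of 0.30 is 0.873, against 0.87 stated, and the other five entries also agree. Nothing below bears on them.

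**Step 1: share delivered,** f = fractions given / total fractions.
- 3 fractions: 2/3 = 66.7%, or 26.7 to 36.0 Gy at prescription level.
- 5 fractions: 3/5 = 60.0%, or 24.0 to 32.4 Gy.

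**Step 2: tissue already at 15 Gy.** This holds where the planned total P is at least 15/f.
- 3 fractions: 15/(2/3) = 22.5 Gy.
- 5 fractions: 15/(3/5) = 25 Gy.

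**Step 3: tissue that can still be spared.** Tissue planned to between 15 and 22.5 Gy (3 fractions) has received 10 to 15 Gy. Tissue planned to between 15 and 25 Gy (5 fractions) has received 9 to 15 Gy. Below those upper limits it can still finish under 15 Gy if the remaining fractions add little.

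**Step 4: whole-plan score against deliverable dose.** Let R be the re-optimized whole-course dose. The deliverable total is T = f × P + (1 − f) × R. These are invented voxels for a 3-fraction course:

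| P (Gy) | R (Gy) | Plan versus plan | T (Gy) | Deliverable result |
|---|---|---|---|---|
| 24 | 12 | spared | 16 + 4 = 20 | not spared |
| 21 | 9 | spared | 14 + 3 = 17 | not spared |
| 18 | 6 | spared | 12 + 2 = 14 | spared |
| 6 | 18 | newly exposed | 4 + 6 = 10 | not exposed |

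The errors run in both directions, and some voxels are scored correctly.

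**Step 5: the alternative without summation.** Suppose only the remaining fractions are re-optimized and scored alone. The last of 3 fractions carries 40/3 = 13.3 Gy to 54/3 = 18.0 Gy at prescription level. At 40 Gy even the prescription level is below 15 Gy, so nearly all tissue would appear spared. Of the three readings, only delivered plus remaining dose, scored cumulatively, answers section 4.6.

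**Step 6: timing wording.** If *at* in the calendar means before that fraction is given, f becomes 1/3 or 2/5, and the limits in Step 2 become 15/(1/3) = 45 Gy and 15/(2/5) = 37.5 Gy. If it means the same visit after delivery, nothing changes.

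**Step 7: direction of the 5% rule.** Section 4.6 seeks less functional liver above 15 Gy. Section 13.8 counts a reduction in functional liver below 15 Gy. Within a fixed total, less liver below the line means more above it, so the rule read literally rewards the opposite of the endpoint.

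**The case against.** The strongest reply is that section 13.8 is silent and does not exclude delivered dose. Re-optimizing the remaining fractions on top of what was given fits the text, and fits section 4.6 better than a whole-course comparison. That stands, and it is why the point is put as a missing instruction. It does not close the gap, because nothing in the text leads an analyst to sum the dose.

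Second, exploratory objective 3 in section 4.3 asks only how often the HIDA scan changes significantly midway. Re-optimization can serve as a yardstick for that without any dose sum. This also stands: the criticism applies to the endpoint wording in 4.6 and the adaptive-feasibility remark in 13.8, not to the objective.

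Third, the stakes are low. The analysis is exploratory and retrospective, no treatment or decision rule depends on it, and section 13.1 lets analysis details change without an amendment unless a significant feature is altered. That limits the weight of the point but does not make the rate interpretable as written.

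A reader might go further and infer that the endpoint measures an adaptation that could never have happened. The documents do not support that: 33% to 40% of the dose remains under section 8.3, and the tissue in Step 3 can still be kept below 15 Gy.

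**Conclusion.** The point holds as a specification gap with a definite consequence. Read literally as plan versus plan, section 13.8 can credit sparing of tissue that has already reached 15 Gy (planned to at least 22.5 Gy in 3 fractions or 25 Gy in 5). It can also charge as exposed tissue that would stay below 15 Gy. These limits rest on the section 8.3 timing and on equal fractions. The reversed inequality in 13.8 is a separate contradiction with 4.6 in the same sentence.

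The size and net direction of the error cannot be computed, since the documents give no dose-volume data. A reader might try to size it by assuming that the volume receiving at least dose D falls as D to the power −k. With k from 0.5 to 2, the share of the planned 15 Gy volume already at 15 Gy would be 44% to 82% (3 fractions) or 36% to 77% (5 fractions). Those figures should not be read as bias. The fall-off is assumed, the volume includes the target, whose coverage is fixed across plans (section 9.1), and a voxel already at 15 Gy causes an error only if the re-optimized plan claims to bring it below the line. Nor do the documents show that the correct rate would be lower.

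No primary result or sample size is affected. The change is worth making because it is cheap and decides what the rate means.

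**What to change.** In section 13.8:

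1. Define the adapted dose as the fractions already delivered on the original plan plus the remaining fractions on the re-optimized plan.
2. Name the comparator: the original plan for all fractions.
3. Score both on the mid-treatment HIDA scan, using the cumulative 15 Gy line.
4. Apply the 5% rule to the reduction in functional liver receiving more than 15 Gy, correcting the inequality in 13.8 to agree with 4.6. Without this, the dose sum would still be scored in the wrong direction.

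Reconcile the timing in section 8.3 with footnote A of the study calendar. Record the number of fractions delivered at each midway scan and use that number in the sum.

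Cost: one dose summation per subject and a few sentences of text, with no extra scan or patient. The downside is that the reported adaptation rate may change.
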